8.5 Pregnancy and Pregnancy Outcomes

Pregnant females are excluded from this study. If participants become pregnant at any time during the course of the study, participants will be offered the option to remain in the study, but off of study product, per Section 7.5.2.

Pregnancy-related data will be collected using pregnancy CRFs for all pregnancies detected during the study. Pregnancy outcomes will not be expeditiously reported to IPM, DAIDS MO, and NICHD MO unless there is an associated AE in the pregnant participant that meets expedited reporting criteria or the pregnancy results in a

congenital anomaly meeting International Conference on Harmonisation (ICH) guidelines for expedited reporting.

8.6 Regulatory Requirements

Information on all reported CRFs will be included in reports to the FDA and other applicable government and regulatory authorities. Site loRs/designees will submit AE information in accordance with local regulatory agencies' or other local authorities' requirements. Site loRs/designees also will submit AE information and any other relevant safety information to their IRBs in accordance with IRB requirements.

In addition, as per local regulatory directives, any staff member who has a reasonable cause to believe that any child with whom he/she comes in contact has suffered abuse, or that any person with whom the staff member comes in contact has abused a child, may be required to immediately report their concerns to authorities.

8.7 Social Harms Reporting

Although study sites make every effort to protect participant privacy and confidentiality, it is possible that participants' involvement in the study could become known to others and that social harms (e.g., intimate partner violence, discrimination, stigmatization, etc.) may result. Social harms that are judged by the loR/designee to be serious or unexpected will be reported to the PSRT and responsible site IRBs according to their individual requirements.

9 CLINICAL MANAGEMENT

Guidelines for clinical management and temporary product hold/permanent discontinuation of study product are outlined in this section. In general, the loR/designee has the discretion to hold study product temporarily at any time if s/he feels that continued product use would be harmful to the participant or interfere with treatment deemed clinically necessary. Unless otherwise specified below, the loR/designee must immediately consult the PSRT for further guidance on resuming study product, continuing the hold temporarily, or progressing to permanent discontinuation of study product. The loR/designee will document all temporary product holds and permanent discontinuations on applicable CRFs.

9.1 Grading System

AE severity grading is described in Section 8.4.3.

9.2 Dose Modification Instructions

No dose modifications will be undertaken in this study.

9.3 General Criteria for Temporary Hold and Permanent Discontinuation of Study Product

A participant will be permanently discontinued or a temporary hold may be initiated from VR product use by the IoR/designee for any of the following reasons:

- Acquisition of HIV-1 infection; such participants will not resume product use at any time. The study VR must be held beginning immediately upon recognition of the first reactive rapid HIV test. If, via the algorithm in Appendix II, the participant is determined to be HIV-uninfected, she may resume product use. The loR/designee must permanently discontinue the study VR if HIV-1 infection is confirmed. (Permanent Discontinuation)
- Allergic reaction to the VR (Permanent Discontinuation)
- Pregnancy (Permanent Discontinuation)
- Breastfeeding (Permanent Discontinuation)
- Reported use of PEP for HIV exposure (Permanent Discontinuation)
- Reported use of PrEP for HIV prevention (Permanent Discontinuation)
- Non-therapeutic injection drug use (Permanent Discontinuation)
- Report of an HIV-positive partner (Permanent Discontinuation)
- Participant is unable or unwilling to comply with required study requirements, or otherwise might be put at undue risk to their safety and well-being by continuing product use, according to the judgment of the IoR/designee
 - The IoR/designee must consult the PSRT on all temporary product holds for this reason for further guidance on resuming product use, continuing the temporary hold, or progressing to permanent discontinuation.
 - If product use is temporarily held/permanently discontinued for this reason, but the underlying reason for the temporary hold later resolves, the loR/designee must consult the PSRT to resume product use at that time.

9.4 Temporary Product Hold/Permanent Discontinuation in Response to Adverse Events

Grade 1 or 2

In general, a participant who develops a Grade 1 or 2 AE not specifically addressed below, regardless of relationship to study product, may continue product use.

Grade 3

Participants who develop a Grade 3 AE not specifically addressed below, judged by the IoR/designee to be not related to study product, may continue product use.

In general, for participants who develop a Grade 3 AE not specifically addressed below, judged by the IoR/designee to be related to study product, and unless otherwise decided in consultation with the PSRT, the IoR/designee must:

- Temporarily hold the study product
- Re-evaluate the participant at least weekly for up to 2 weeks

- Resume study product if improvement to ≤ Grade 2 is documented within 2 weeks
- Consult PSRT regarding further product management if improvement to severity ≤ Grade 2 cannot be documented within 2 weeks

If product use is resumed and the same Grade 3 AE deemed related to study product, recurs at any time, the IoR/designee must temporarily hold study product and consult the PSRT for further guidance on continuing the temporary hold or progressing to permanent discontinuation of the study product.

Grade 4

Participants who develop a Grade 4 AE (regardless of relationship to study product), that is not specifically addressed below, must have the study product held. The IoR/designee must consult the PSRT and continue the temporary product hold until a recommendation is obtained from the PSRT.

9.5 Genital Sexually Transmitted Infection/Reproductive Tract Infection

The IoR/designee must manage STI/RTI per current CDC guidelines, available at http://www.cdc.gov/std/treatment/.

VR use need not be held in the event of an STI/RTI requiring treatment, unless other temporary product hold/permanent discontinuation guidelines apply. Should the IoR/designee determine that a temporary product hold is warranted, consultation with the PSRT is required.

A thorough evaluation of genital complaints is expected in the context of this study; however, syndromic management of genital symptoms is acceptable while awaiting laboratory results if such practice is in line with the local standards of care. It is recommended that treatment includes first-line oral or parenteral (in the case of syphilis or gonorrhea, for example) medications, when at all possible.

9.6 Management of Specific Genital Events

If a suspected finding is reported by the participant between scheduled visits, an interim visit may be scheduled at the discretion of the Site Investigator. Management of genital events observed at scheduled or interim visits will be in accordance with the following:

Superficial epithelial disruption

- Continue study VR use
- Perform naked eye evaluation
- Re-evaluate by speculum examination in approximately 3-5 days
- If condition worsens temporarily hold study VR use and consult the PSRT; otherwise continue study VR use

Deep epithelial disruption

• Temporarily hold study product

- Re-evaluate in approximately 3-5 days and resume study VR use if resolved
- If unresolved at approximately 3-5 days, re-evaluate within approximately 2-3 days. If resolved at that time, may resume study VR use. If unresolved at this second reevaluation, continue temporary product hold, consult with PSRT regarding permanent discontinuation, and provide care per local standard
- If there is reoccurrence with no identified etiology, continue temporary product hold and consult the PSRT regarding permanent discontinuation

Localized erythema or edema: area of less than 50% of vulvar surface or combined vaginal and cervical surface affected by erythema or edema

- Continue study VR use
- Perform naked eye evaluation
- Re-evaluate in approximately 3-5 days
- If condition worsens, temporarily hold study VR use and consult the PSRT; otherwise continue study VR use

Generalized erythema or severe edema: area of more than 50% of vulvar surface or combined vaginal and cervical surface affected by erythema or severe edema

- Temporarily hold study product
- Perform naked eye evaluation
- Re-evaluate in approximately 3-5 days and reinstate study VR use if resolved
- If unresolved at approximately 3-5 days, re-evaluate within approximately 2-3 days. If resolved at that time, study product use may resume. If unresolved at this second reevaluation, continue temporary product hold, consult with PSRT regarding permanent discontinuation, and provide care per local standard

Unexpected genital bleeding (See SSP for definition)

- Continue study VR use
- Perform naked eye evaluation
- If determined to be due to deep epithelial disruption, refer to guidelines above; otherwise continue study VR use

Cervicitis (including findings on exam such as inflammation and/or friability)

- Treat for cervicitis and temporarily hold study product
- Evaluate for GC/CT;
- Re-evaluate in approximately 3-5 days. If all symptoms and signs are resolved at that time, resume study VR use

Genital petechia(e)

- Continue study VR use
- Perform naked eye evaluation
- No further evaluation or treatment is required

Genital ecchymosis

- Continue study VR use
- Perform naked eye evaluation
- No further evaluation or treatment is required

9.7 HIV-1 Infection

A participant who has a positive test for HIV-1 must have study product held. If the participant is subsequently determined to be HIV-negative according to the algorithm in Appendix II, study product may be resumed. If HIV-1 infection is confirmed, study product will be permanently discontinued by the IoR/designee. A participant who is confirmed to be HIV-1 positive during the course of the study will have study product discontinued and will be followed, as per Section 7.5.1.

9.8 Pregnancy

All study participants are required to be using an effective method of contraception according to Section 5.2. Study staff will provide contraceptive counseling to enrolled participants throughout the duration of study participation and will facilitate access to contraceptive services through direct service delivery. Study staff also will provide participants with condoms and counseling on use of condoms ideally during every sex act during study participation.

Pregnancy testing is performed at all study visits and may be performed as indicated at interim visits. In addition, participants are encouraged to report all signs or symptoms of pregnancy to study staff. The IoR/designee will counsel any participant who becomes pregnant regarding possible risks to the fetus according to site SOPs. The IoR/designee also will refer the participant to all applicable services; however, sites will not be responsible for paying for pregnancy-related care.

A participant who is pregnant at the Final Clinic Visit will continue to be followed until the pregnancy outcome is ascertained (or, in consultation with the PSRT, it is determined that the pregnancy outcome cannot be ascertained). Pregnancy outcomes are reported on relevant CRFs; outcomes meeting criteria for EAE reporting also are reported on EAE forms.

A participant who becomes pregnant during the course of the study will have study product discontinued and will be followed, as per Section 7.5.2.

A participant who becomes pregnant during the course of study participation may be offered participation in MTN-016, HIV Prevention Agent Pregnancy Exposure Registry: EMBRACE Study, at sites participating in MTN-016. This registry study captures pregnancy outcomes as well as infant health information, (including growth), to evaluate the safety and teratogenic risks of microbicide and oral PrEP exposure in pregnancy. In the event that a study site is not taking part in MTN-016, participants may be contacted to collect pregnancy outcomes.

For additional details regarding obtaining pregnancy outcome, please reference the MTN-023/IPM 030 SSP Manual (www.mtnstopshiv.org).

9.9 Criteria for Early Termination of Study Participation

Participants may voluntarily withdraw from the study for any reason at any time. The loR also may withdraw participants from the study to protect their safety and/or if they are unwilling or unable to comply with required study procedures, after consultation with the PSRT. Participants also may be withdrawn if the study sponsors, the MTN LOC, IPM, government or regulatory authorities, including the FDA and Office for Human Research Protections (OHRP), or site IRBs/ECs terminate the study prior to its planned end date. Every reasonable effort is made to complete a final evaluation of participants who withdraw or are withdrawn from the study prior to completing follow-up. Study staff members will record the reason(s) for all withdrawals in participants' study records. In the event that participants who voluntarily withdraw from the study wish to re-join the study, they may resume product use (if applicable) and follow-up through their originally scheduled study exit date, pending consultation with the PSRT.

10 STATISTICAL CONSIDERATIONS

10.1 Overview and Summary of Design

This is a multi-site, double-blinded, two arm, 3:1 randomized, placebo-controlled trial to assess the safety of dapivirine (25 mg) administered in a silicone elastomer vaginal ring, when inserted once every 4 weeks during 24 weeks of study product use by healthy, HIV-uninfected, sexually experienced, adolescent females, 15 - 17 years old (inclusive), as compared with a placebo VR. A total of approximately 96 adolescent females (72 in the dapivirine VR arm and 24 in the placebo VR arm) will be randomized.

10.2 Study Endpoints

Primary Endpoints

Consistent with the primary study objective to assess the safety of dapivirine (25 mg) administered in a silicone elastomer vaginal ring, when inserted once every 4 weeks during 24 weeks of study product use by healthy, HIV-uninfected, sexually experienced, adolescent females, 15 - 17 years old (inclusive), as compared with a placebo, the primary safety endpoints are the proportion of females in each of the two arms with:

• Grade 2 adverse events as defined by the Division of AIDS Table for Grading the Severity of Adult and Pediatric Adverse Events, Version 1.0, Dec 2004 (Clarification dated August 2009), Addendum 1, (Female Genital Grading Table for Use in Microbicide Studies) judged to be related to study product

• Grade 3 or higher adverse events as defined by the Division of AIDS Table for Grading the Severity of Adult and Pediatric Adverse Events, Version 1.0, Dec 2004 (Clarification dated August 2009)

Secondary Endpoints

Consistent with the secondary study objective to evaluate the acceptability of the study VR (dapivirine or placebo) in HIV uninfected adolescent females, when inserted once every 4 weeks for a 24 week period, the following endpoint will be assessed:

• Participant's self-report on multiple components of acceptability via attitudinal questions

To evaluate adherence to the study VR (dapivirine or placebo) in HIV uninfected adolescent females, when inserted once every 4 weeks for a 24 week period the following endpoints will be assessed:

- Frequency of VR removals and expulsions
- Dapivirine concentrations in plasma and vaginal fluid

Consistent with the secondary study objective to evaluate the systemic and local dapivirine exposure, the following endpoint will be assessed:

• Dapivirine concentrations in plasma and vaginal fluid

Exploratory endpoints

- Participant's self-report on multiple components of acceptability via attitudinal questions
- Frequency of VR removals and expulsions
- Dapivirine concentrations in plasma and vaginal fluid
- Residual amount of dapivirine measured in returned VRs
- Vaginal pH, microflora and biomarkers

10.3 Primary Study Hypothesis

MTN-023/IPM 030 hypothesizes that a dapivirine VR will be as safe and well tolerated as the placebo VR.

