10.4 Sample Size and Power Calculations

10.4.1 Primary Endpoints

The proposed total sample size is approximately N=96 adolescent females randomized to two arms in a 3:1 ratio giving 72 adolescent females in the dapivirine VR arm and 24

adolescent females in the placebo VR arm. The sample size is based upon the size of similar Phase 2a studies of vaginal microbicide products and includes a 3:1 ratio of drug to placebo arms to allow for the collection of additional safety endpoints in the drug arm while maintaining blinding between arms.

As a means to characterize the statistical properties of this study Table 13 presents the probability (expressed as a percent) of observing zero, at least one, and two or more safety endpoints among the 72 adolescent females in the dapivirine VR arm for various 'true' event rates.

Event Rate (%)	P (0 events n=72) (%)	P (> 1 event n=72) (%)	P (> 2 events n=72) (%)
0.5	69.7	30.3	5.1
1.0	48.5	51.5	16.2
3.5	7.7	92.3	72.2
5	2.5	97.5	88.1
10	0.05	99.95	99.5
15	0.0	99.99	99.99

An alternative way of describing the statistical properties of the study design is in terms of the true rate based on the observed data. Table 14 shows the exact 2-sided 95% confidence intervals for the probability of an event based on a particular observed rate. For example, if none of the 72 participants using the dapivirine VR experiences a safety event, the 95% exact 2-sided confidence interval for the true rate of event is (0.0%, 4.99%). If we see 2 events, this changes to (0.34%, 9.68%).

 Table 13: Exact Two-sided 95% Confidence Intervals Based on Observing a Particular Rate of Safety Endpoints for Arms of Size 72

Observed event rate, percentage (fraction)	Confidence interval (%)
0.0 (0/72)	(0.0, 4.99)
1.4 (1/72)	(0.04, 7.50)
2.8 (2/72)	(0.34, 9.68)

The primary aim of the study is to compare the safety between the two arms (dapivirine VR arm versus placebo VR arm). Assuming a two-sided Fisher's Exact test with α =.10 and 80% or 90% power, Table 15 provides the difference in the rates of safety events (proportion of females experiencing the safety event of interest) between the dapivirine VR arm and the placebo VR arm that is detectable for a given rate in the placebo VR arm. For example, if the true rate of a given toxicity endpoint in the placebo VR arm is 4.2% (1 out of 24 females experiencing a safety event); the proposed sample size provides 90% power to detect safety endpoint rates greater than 30.2% (26.3% with 80% power).

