10.8.2 Primary Analysis

When the use of descriptive statistics to assess group characteristics or differences is required, the following methods will be used: for categorical variables, the number and percent in each category; for continuous variables, the mean, median, standard deviation, quartiles and range (minimum, maximum). Within-treatment group assessment of the change from the baseline measurement to a follow-up measurement will be analyzed using McNemar's test (for categorical response variables) or the paired t-test or Wilcoxon signed-ranks test (for continuous variables). When use of formal testing to assess differences between users of the placebo VR and users of the dapivirine VR is required, the following methods will be used: for binomial response variables, chi-square tests and logistic regression (or exact testing methods); for continuous variables, t-tests and linear regression or nonparametric methods if data are non-Normal.

To assess the adequacy of the randomization, participants in each of the two arms will be compared for baseline characteristics including demographics and laboratory measurements using descriptive statistics.

Safety Endpoints

All females randomized into the study will be included in the primary analysis according to principle of Intent-to-Treat. To assess safety, the number and the percentages of participants experiencing each safety endpoint will be tabulated by study arm. Each participant will contribute once in each category (i.e., only for the highest severity AE for each participant) for the calculation of event rates. Exact binomial confidence intervals will be calculated for each safety endpoint for each arm and Fisher's exact test used to test for differences in event rates between the two arms.

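### The primary hypothesis is worded as similarity to placebo, but the planned between-arm analysis is a test for difference, with no margin and no interval for the safety difference

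*Protocol*

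**What the plan says.** Section 10.3 gives the primary hypothesis: "a dapivirine VR will be as safe and well tolerated as the placebo VR". Section 10.4.1 adds: "The primary aim of the study is to compare the safety between the two arms". The arms are "72 in the dapivirine VR arm and 24 in the placebo VR arm" (section 10.1).

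For the primary safety endpoints, section 10.8.2 tabulates counts and percentages by arm and then says: "Exact binomial confidence intervals will be calculated for each safety endpoint for each arm and Fisher's exact test used to test for differences". The general list of between-arm methods in the same section also consists of tests for difference: "for binomial response variables, chi-square tests and logistic regression (or exact testing methods").

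The detectable differences in section 10.4.1 assume a "two-sided Fisher's Exact test with α =.10 and 80% or 90% power". At a true placebo rate of 4.2%, "the proposed sample size provides 90% power to detect safety endpoint rates greater than 30.2% (26.3% with 80% power").

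Two other places bear on the point. Section 2.8.1 states the study hypothesis without a comparator: it predicts only that the ring will prove safe and tolerable in this population. Section 10.8.3 plans a between-arm difference with a 95% confidence interval for adherence, a secondary endpoint. Nothing equivalent is planned for safety.

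**The concern.** The hypothesis claims similarity, while the null hypothesis of the planned test is no difference. If the test rejects because events are more frequent on dapivirine, the hypothesis is contradicted. If it does not reject, the hypothesis has not been shown, because with 24 placebo participants non-rejection is compatible with a substantial excess. An interval for the difference would show how large an excess remains possible. The plan provides only separate intervals for the two arms, and a reader cannot take the interval for the difference directly from those. These are adolescent safety data meant to stand beside adult efficacy results (section 2.8.2), so the form of the safety conclusion matters.

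**Working it through.** **Inputs.** Arms of 72 and 24 (10.1); two-sided Fisher's exact test at 0.10 and a placebo rate of 4.2%, i.e. 1/24 (10.4.1); the protocol's 75% retention scenario of 54 and 18 (10.4.1). The protocol states no safety margin.

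**Step 1: reproduce the protocol's figures.** Exact power is

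Power(p_P, p_D) = Σ_i Σ_j Bin(i; 24, p_P) · Bin(j; 72, p_D) · 1[Fisher p(i, j) ≤ 0.10].

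At p_P = 4.2%, power is 80.3% for p_D = 26.3% and 90.2% for p_D = 30.2%. Across all five rows of the detectable-difference table for 72 versus 24, the 80% column gives 79.7–80.3% and the 90% column 89.9–90.2%. The protocol's figures are right.

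**Step 2: same formula, smaller increases, placebo rate 4.2%.**

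| True dapivirine rate | Power, 72 vs 24 | Power, 54 vs 18 |
|---|---|---|
| 8.3% (doubled) | 3.4% | 1.4% |
| 12.5% (trebled) | 16% | 6% |
| 16.7% (quadrupled) | 37% | 21% |

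At full retention a quadrupled rate gives a non-significant result about 63% of the time (100 − 37). With a placebo rate of 8.3%, power for the same three multiples is 16%, 49% and 80%, so the weakness is greatest when events are rare.

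**Step 3: what an interval for the difference would show.** Newcombe's interval combines the Wilson limits (l, u) of each arm, with d = p_D − p_P:

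lower = d − √[(p_D − l_D)² + (u_P − p_P)²]; upper = d + √[(u_D − p_D)² + (p_P − l_P)²].

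For 3/72 versus 1/24 (both 4.17%, d = 0), the 95% Wilson limits are 1.43% to 11.55% and 0.74% to 20.24%. In percentage points:
- upper = √[(11.55 − 4.17)² + (4.17 − 0.74)²] = √(7.38² + 3.43²) = +8.1
- lower = −√[(4.17 − 1.43)² + (20.24 − 4.17)²] = −√(2.74² + 16.07²) = −16.3

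| Observed (identical rates) | 95% interval, points | 90% interval, points |
|---|---|---|
| 3/72 vs 1/24 | −16.3 to +8.1 | −12.8 to +6.6 |
| 6/72 vs 2/24 | −18.1 to +10.6 | −14.5 to +8.9 |
| 15/72 vs 5/24 | −21.1 to +15.8 | −17.6 to +13.6 |

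Fisher's p is 1.0 in all three rows. The p-value does not distinguish among them; the interval does.

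**Step 4: could a margin be added instead?** The margins here are assumed, because the protocol gives none. With equal true rates p, 3:1 allocation, one-sided 5% and 80% power,

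n_P = (1.645 + 0.842)² · p(1 − p)(1 + 1/3) / margin², total = 4·n_P.

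At p = 4.2% and a 10-point margin: 6.18 × 0.0402 × 1.333 / 0.01 ≈ 33.2, so 34 placebo participants and 136 in total. Margins of 5, 10 and 15 points need totals of 532, 136 and 60 at p = 4.2%, and 1004, 252 and 112 at p = 8.3%. The normal approximation is rough at such low rates. Even so, 96 participants could support a similarity claim only against a margin of about 15 points or more, and only if events are rare.

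**The case against.** The strongest reply is that this is a small Phase 2a study that hides nothing. Section 10.4.1 bases the size on similar studies, explains the 3:1 ratio by the wish for more safety information on the active ring, tabulates single-arm precision for 72 participants, and prints the large detectable differences. Section 2.8.1 and the primary objective in section 3.1 can be read without a comparator. Margins, extra interval columns and rules of interpretation are often left to a statistical analysis plan, which is not shown. All of this stands, and it rules out any criticism of the sample size. It does not remove the point, because the similarity hypothesis, the comparative primary aim and the test for difference are all fixed in the protocol and do not fit together.

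Three stronger readings are tempting and not supported:
- **That a non-significant result will be taken as confirmation.** A reader might infer this, but no section says so; the protocol simply has no rule of interpretation.
- **That the test will probably be non-significant however harmful the ring is.** With placebo at 4.2%, power is 28% at a dapivirine rate of 15% but 54% at 20%, 76% at 25% and 80% at 26.3%. Non-rejection is the likelier result only for the smaller increases.
- **That a borderline example proves the case.** An observed 14/72 versus 1/24 gives p = 0.105 and a 95% interval of −2.5 to +26.4 points. One more dapivirine event gives p = 0.065, and the 90% interval for 14/72, which matches the planned alpha, is +1.2 to +24.6 and excludes zero. The example sits on the boundary and should carry no weight.

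**Conclusion.** The mismatch is real and should be corrected. A non-significant Fisher test cannot support the hypothesis in section 10.3, and at a placebo rate of 4.2% it is the likely outcome even when the true rate is trebled or quadrupled (power 16% and 37%). These figures assume full retention and the two-sided 0.10 level of section 10.4.1; at 54 versus 18 they are lower. The finding concerns wording and the form of the primary result. It is not an error in the power tables, and it does not show that the trial is uninformative about the ring's safety, since the per-arm counts and intervals remain useful. An unseen analysis plan might already add the interval, but the protocol's hypothesis would still need rewording.

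**What to change.** In section 10.8.2, make the difference in event proportions (dapivirine minus placebo) with its confidence interval the main between-arm result for both primary endpoints. State the interval method and level: either 95%, or 90% to match the planned alpha of 0.10. The choice matters near the boundary, so it should be made in advance. Keep Fisher's test as supportive.

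In section 10.3, reword the hypothesis as estimation of the safety difference, consistent with section 2.8.1. Add that a non-significant test will not be reported as showing equal safety. Reading a conclusion from the upper limit alone would not be a decision rule, because no margin is set. If the sponsor wants to keep a similarity claim, it must prespecify and justify a margin and accept the sample size that follows.

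The cost is a few sentences and one table column, with no change to participants, visits or treatment. The drawback is that the interval will be visibly wide and the conclusion correspondingly less favourable.
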